## 10. Pharmacokinetics

### 10.1. Pharmacokinetic Data Handling

Plasma concentrations that are below the limit of quantification (BLQ) will be treated as zero for calculation of descriptive statistics and all PK analyses. Missing concentrations will be excluded from all calculations.

All concentrations and PK parameters will be rounded to 3 significant figures for reporting purposes. The only exceptions will be actual sampling times and  $T_{max}$  (which will be rounded to 2 decimal places) and the number of data points (which will be reported as integers). Summary statistics will be rounded to the same precision as individual data, with the exception of  $n$  (which will be reported as an integer). Estimates and confidence intervals from all statistical comparisons will be reported to 2 decimal places, and associated p-values will be reported to 4 decimal places.

### 10.2. Plasma Pharmacokinetic Concentrations

Serial blood samples (5 mL) for PK assessment of SKI-O-592 and its metabolites (M2 and M4) will be collected from all subjects in the PK/PD subset at the following time points:

- Day 1: 0 hour (morning pre-dose), and at 0.25, 0.5, 1, 2, 4, 8 and 12 hours morning post-dose (12-hr sample should be collected prior to the evening dose).
- Week 12 (Day 84): 0 hour (morning pre-dose), and 0.25, 0.5, 1, 2, 4, 8, and 12 hours.

In addition, PK samples will also be collected at the following time points on Day 8 from subjects in the safety run-in period only:

- Day 8: 0 hour (morning pre-dose), and at 0.25, 0.5, 1, 2, 4, 8 and 12 hours morning post-dose (12-hr sample should be collected prior to the evening dose).

In all non-PK/PD subset subjects, trough PK samples will be collected during Week 12 only, for these samples plasma concentrations of SKI-O-592, M2, and M4 will be presented in data listings.

Individual plasma concentrations of SKI-O-592, M2, and M4 will be presented from the PK/PD subset in data listings and presented graphically versus actual time by treatment and analyte on both linear and semi-logarithmic scales.

Plasma concentrations of SKI-O-592, M2, and M4 will be summarized using descriptive statistics (n, mean, SD, CV, minimum, median, and maximum) by time point for each treatment and day separately. Mean plasma concentrations will be plotted by treatment for each analyte versus nominal time on both linear and semi-logarithmic scales.

### 10.3. Plasma Pharmacokinetic Parameters

The following plasma PK parameters will, where possible, be estimated on Days 1, 84 and 8 (for the first 5 subjects enrolled in the safety run-in period) for SKI-O-592, M2, and M4 using actual sampling times via non-compartment analysis using Phoenix WinNonlin version 6.4 or higher:

$C_{trough}$	Trough concentration observed at steady state (Day 8 and 84 only).
$C_{max}$	Maximum observed concentration.
$T_{max}$	Time of the maximum observed concentration.
$AUC_{0-\tau}$	Area under the concentration versus time curve within a dosing interval ( $\tau$ ), calculated using the linear trapezoidal rule.
$t_{1/2,eff}$	Effective half-life, calculated as $[\ln(2)/((-ln(1-(1/R_{AUC}))/\tau))]$ (Day 8 and 84 only).
$R_{met}$	Metabolite ratio, calculated as $[(AUC_{0-\tau} \text{ (metabolite)}) / (AUC_{0-\tau} \text{ (parent)})]$ .
$R_{AUC}$	Accumulation ratio based, calculated as $[AUC_{0-\tau} \text{ (Day 8 and 84)} / AUC_{0-\tau} \text{ (Day 1)}]$ .

Actual PK blood sampling times will be used for the assessment of all PK parameters. Plasma PK parameters for SKI-O-592, M2, and M4 will be presented in data listings and summarized separately using the following descriptive statistics for each treatment and analyte (n, geometric mean, geometric CV, mean, SD, CV, minimum, median, and maximum). For  $T_{max}$ , only n, median, minimum and maximum will be reported.

Note: due to the limited duration of sampling after each dose (i.e. 12 hours), parameters associated with the estimation of a terminal elimination phase (e.g.,  $K_{el}$ ,  $t_{1/2}$ ,  $CL/F$ ,  $V_z/F$ ,  $AUC_{0-\infty}$ , etc.) will not be presented.

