Systemic exposure (C_{max} and $AUC_{0-\tau}$) to SKI-O-592, M2, and M4 at 400 mg BID is predicted to be higher using the second approach [PK Parameter (200 mg BID, Day 7) \times 2]. For SKI-O-592, C_{max} and $AUC_{0-\tau}$ are predicted to be 6160 ng/mL and 14600 h ng/mL, respectively, and for M2 C_{max} and $AUC_{0-\tau}$ are predicted to be 994 ng/mL and 10000 h ng/mL, respectively, which is well within exposure levels calculated at the NOAEL in rats, and comparable to levels previously observed at 800 mg in Study OSCO-P1201. However, due to the very low M4 metabolite ratios observed in rats compared to healthy volunteers, predicted exposure to M4 (644 ng/mL and 1970 h ng/mL for C_{max} and $AUC_{0-\tau}$, respectively) is higher than the NOAEL exposure. Therefore, the dosing regimens proposed for this study (200 mg BID and 400 mg BID) have been carefully selected to ensure that exposure to M4 does not exceed levels observed previously in healthy volunteers (Study OSCO-P1201, 800 mg).

*Note: Because increases in systemic exposure to M4 were less than proportional to the dose of SKI-O-703 in Studies OSCO-P1201 and OSCO-P1202, and a reduction in M4 levels was observed over time in Study OSCO-P1202, both means of estimating C_{max} and $AUC_{0-\tau}$ for M4 at 400 mg BID are considered to be cautious approaches, potentially overestimating exposure at 400 mg BID. An interim safety and PK data review will be performed by the DMC for the first 5 subjects dosed (including 2 subjects dosed with 400 mg BID) before the remaining subjects are treated.

Following single oral administration of 400 mg SKI-O-703 (Study OSCO-P1203), overall systemic exposure to SKI-O-592, M2 and M4 (AUC_{0-t} and $AUC_{0-\infty}$) was comparable between the fed and fasted state, with 90% CI for the ratio (Fed / Fasted) contained entirely within the BE limits (0.80, 1.25) for SKI-O-592 and M4. By contrast, when administered in the fed state there was an approximate 56%, 43% and 46% reduction in maximum exposure (C_{max}) for SKI-O-592, M2 and M4, respectively, with an associated 2.5 to 4 hours delay in median T_{max} across all analytes. Since the overall extent of absorption is unaffected by the intake of food, but peak exposure is reduced, dosing is recommended with food in this

Phase 2 study to reduce the potential for AEs which may be associated with spikes (i.e. high C_{max}) in SKI-O-592, M2 and M4.

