## **10.4. Pharmacokinetic Statistical Analyses**

### **10.4.1. Assessment of Accumulation**

The accumulation ratio will be estimated by making comparisons of  $AUC_{0-\tau}$  and  $C_{max}$  on Day 84 with corresponding estimates on Day 1 for each treatment separately; a mixed-effects model will be fitted to log-transformed  $AUC_{0-\tau}$  and  $C_{max}$  including day (Day 1 or 84) as a fixed effect and subject as a random effect. This model will be used to estimate the accumulation ratio (Day 84 / Day 1) with 95% CIs for each treatment. The geometric least squares means and ratio with 95% CIs will be calculated by treatment and parameter.

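### Effective half-life is calculated per subject by a formula with no value at R_AUC of 1 or less, so summarising only the calculable values biases it upward when accumulation is near 1

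*SAP*

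**What the plan says.** SAP 10.3 opens with "The following plasma PK parameters will, where possible, be estimated on Days 1, 84 and 8", and covers SKI-O-592, M2 and M4. Day 8 applies to the run-in subjects only. Two of the listed parameters matter here:

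- R_AUC ("Accumulation ratio based, calculated as" AUC0-tau on Day 8 or 84 divided by AUC0-tau on Day 1).
- t1/2,eff ("Effective half-life, calculated as" ln2/(−ln(1−1/R_AUC)/tau)), for Days 8 and 84.

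The parameters "will be presented in data listings and summarized separately using the following descriptive statistics for each treatment and analyte": n, geometric mean and CV, mean, SD, CV, minimum, median and maximum. A note in the same section says that sampling lasts only 12 hours after a dose, so "parameters associated with the estimation of a terminal elimination phase" are not presented. Protocol 6.5.2 had listed t1/2, Kel, CL/F and Vz/F. The effective half-life is therefore the only half-life left.

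SAP 10.4.1 fits a mixed model to log AUC0-tau and log Cmax: "This model will be used to estimate the accumulation ratio (Day 84 / Day 1) with 95% CIs for each treatment". It does not use that ratio for the half-life. Protocol 1.3 notes that "a reduction in M4 levels was observed over time in Study OSCO-P1202". Neither document gives a measured R_AUC for any analyte.

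**The concern.** R_AUC is a ratio of two measured AUCs, and nothing keeps it above 1. When the true ratio is close to 1, ordinary day-to-day variation puts a large share of subjects at or below 1, where the formula has no value. Estimating where possible means dropping those subjects. Whether a subject is dropped depends on the very quantity being estimated, so those who remain are the ones whose variation went upward.

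The resulting mean or median would be read as the half-life in ITP patients. PK is a named secondary objective, and Protocol 3.1.2 says the serial samples should help refine Phase 3 sparse sampling. The formula also assumes that clearance does not change between the first dose and steady state. The protocol's remark on M4 puts that in doubt for this metabolite.

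**Working it through.** The documents state no R_AUC and no half-life, so there is no figure to reproduce.

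**1. Where the formula exists.** With constant clearance and one exponential, R = 1/(1−e^(−k·tau)). Solving for the half-life at tau = 12 h gives t = 12·ln2/(−ln(1−1/R)) = 8.318/(−ln(1−1/R)). At R = 1 the inner logarithm is ln 0, and below 1 it is the logarithm of a negative number. As R falls towards 1 the value tends to 0 h. Above 1: R = 1.1 gives 3.47 h, 1.5 gives 7.57 h, 2.0 gives 12.0 h.

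**2. What R might be.** Protocol 1.3 predicts steady-state Cmax and AUC0-tau at 400 mg BID. Under the same one-exponential approximation, Cmax/Cavg = k·tau/(1−e^(−k·tau)), with Cavg = AUC/12.

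- SKI-O-592: 6160/(14600/12) = 5.06, so k·tau = 5.03 and R = 1.007 (t = 1.65 h).
- SKI-O-592 with the 56% Cmax reduction that Protocol 1.3 reports under food, AUC unchanged: 0.44 × 6160 = 2710; 2710/1217 = 2.23, so R = 1.18 (t = 4.4 h).
- M2: 994/(10000/12) = 1.19, so R = 3.3.
- M4: 644/(1970/12) = 3.92, so R = 1.02. With the 46% food effect: 0.54 × 644 = 348, ratio 2.12, R = 1.21.

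These are crude proxies. They use the shape of one steady-state profile and cannot see a change in clearance since Day 1. The food effect comes from single doses and does not scale to every analyte. For M2 it would give 0.57 × 994 = 567 ng/mL, below the average of 833 ng/mL, which is impossible.

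**3. Effect of dropping undefined values.** Assume a common true ratio R and log-normal, independent errors on the two days. Then ln R_AUC has SD s = √(2·ln(1+CV²)): 0.280 at CV 20% and 0.415 at CV 30%. The CV is an assumption. The undefined share is p = Φ(−ln R/s). The formula rises with R_AUC, so the median of the calculable values is the formula at quantile p + (1−p)/2 of R_AUC.

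Example, R = 1.007 and CV 20%: p = Φ(−0.007/0.280) = 0.49. The quantile is 0.745 (z = 0.659). R_AUC there is 1.007 × e^(0.659 × 0.280) = 1.211, and t = 8.318/1.747 = 4.76 h, against 1.67 h at R = 1.007.

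| True R | t at true R (h) | Undefined | Median of the rest (h) | Ratio |
|---|---|---|---|---|
| 1.007 | 1.67 | 49% | 4.8–5.9 | 2.8–3.5 |
| 1.10 | 3.47 | 37–41% | 5.2–6.4 | 1.5–1.8 |
| 1.18 | 4.4 | 28–35% | 5.7–6.8 | 1.3–1.5 |
| 1.5 | 7.57 | 7–16% | 7.9–8.8 | 1.05–1.16 |
| 2.0 | 12.0 | 1–5% | 12.0–12.4 | 1.00–1.04 |
| 3.0 | 20.5 | under 1% | 20.5–20.6 | 1.00 |

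Ranges run from CV 20% to CV 30%. If the PK/PD subset of at least 20 splits 2:2:1, each active arm has 20 × 2/5 = 8 subjects. About 4 of the 8 would then contribute at R = 1.007, and 5 to 6 at R = 1.18.

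**4. M4.** If the geometric mean ratio is below 1, more than half of the values are undefined by symmetry: 55–57% at 0.95, 60–65% at 0.9, 70–79% at 0.8, 80–90% at 0.7. At ratios of 0.7 to 0.9 the survivors still return a median of 3.6 to 5.4 h, although the formula has no value at the true ratio. At 1.02, 47–48% are undefined; at 1.2, 26–33%.

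**The case against.** The best case for the plan has four parts.

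- Estimation only where possible already permits omission. The listings show individual R_AUC, and an n for t1/2,eff below the n for R_AUC reveals how many values were lost. This stands as far as it goes: an attentive reader could reconstruct the count. It does not correct the mean or median, because the omission is itself the source of the bias.
- The parent ratio of 1.007 comes from healthy-volunteer figures, while this trial doses after food. This stands. The feeding state in OSCO-P1202 is not given, and if it was fasted the implied ratio is nearer 1.18 and the bias about 1.3 to 1.5 times. A reader might infer a roughly threefold error for the parent drug. That is only the upper end of the range, and the documents do not establish it.
- A reader might also infer that the calculation must fail for most M4 values. That rests on one unquantified sentence about healthy volunteers. It follows if the ratio in patients is below 1, but no ratio is stated, and the protocol's own M4 figures would be compatible with one slightly above 1.
- No efficacy test, safety rule or dose decision in the documents uses t1/2,eff, and Protocol 3.1.2 refers to the serial samples, not to this parameter. This stands and limits the weight of the point.

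**Conclusion.** The point holds for how the effective half-life is summarised. The formula is undefined at R_AUC of 1 or less, the SAP has no rule for that case, and summarising the remaining subjects biases the only reported half-life upward when true accumulation is near 1.

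The size is conditional. For SKI-O-592, with a CV of 20–30% and a true ratio of about 1.01 to 1.18, 28–49% of values are undefined and the median is about 1.3 to 3.5 times too long. Both the ratio range and the CV are assumptions. Above a ratio of about 1.5 the effect is small, and for M2 (implied ratio about 3.3) it is negligible. For M4, about half or more would be undefined if the fall seen in volunteers recurs. In that case the constant-clearance assumption fails as well, and any reported value would have no clear meaning. The primary endpoint is untouched.

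**What to change.** In SAP 10.3:

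- Make the summary t1/2,eff for each dose and analyte the formula applied once to the SAP 10.4.1 geometric mean AUC0-tau ratio (Day 84/Day 1) and to its 95% CI limits. The formula is increasing, so the limits transform directly. Report *not estimable* for any estimate or limit of 1 or less, M4 included.
- State in SAP 10.4.1 that the model is fitted by analyte, which the text does not now say.
- Keep individual t1/2,eff values, Day 8 included, in listings only, marked *not calculable* at R_AUC of 1 or less. Summarise individual values only where every subject has R_AUC above 1. This should preserve M2.
- Report the number of subjects with R_AUC of 1 or less, by dose, analyte and day.

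The cost is SAP wording, since the model is already planned. Some results will read *not estimable*. With 8 subjects and s = 0.280, the standard error of the log ratio is 0.280/√8 = 0.099. At a true ratio of 1.18, the expected lower limit is 1.18 × e^(−2.36 × 0.099) = 0.93, so it has no half-life. At 1.007 the group ratio itself would be 1 or less nearly half the time (Φ(−0.007/0.099) = 0.47). That reflects how little these data say about the half-life when accumulation is slight. SAP 10.4.1 does not model Day 8, so there will be no Day 8 summary for the 4 active-treated run-in subjects if any has R_AUC of 1 or less. The formula still assumes constant clearance, so for M4 an estimable value would need that caveat beside it.

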## **10.4. Pharmacokinetic Statistical Analyses**

### **10.4.1. Assessment of Accumulation**

The accumulation ratio will be estimated by making comparisons of  $AUC_{0-\tau}$  and  $C_{max}$  on Day 84 with corresponding estimates on Day 1 for each treatment separately; a mixed-effects model will be fitted to log-transformed  $AUC_{0-\tau}$  and  $C_{max}$  including day (Day 1 or 84) as a fixed effect and subject as a random effect. This model will be used to estimate the accumulation ratio (Day 84 / Day 1) with 95% CIs for each treatment. The geometric least squares means and ratio with 95% CIs will be calculated by treatment and parameter.

## **11. Pharmacodynamics**

### **11.1. Pharmacodynamic Data Handling**

Subjects with baseline CD63+ values below the limit of detection will be defined as low responders and excluded from the PD set and all summaries of PD data. Baseline will be defined as the percentage of activated CD63+ cells at predose samples on Day 1.

All PD data will be rounded to 3 significant figures for reporting purposes. The only exceptions will be actual sampling times and  $TE_{max}$  (which will be rounded to 2 decimal places). Summary statistics will be rounded to the same precision as individual data, with the exception of n (which will be reported as an integer).

### **11.2. Pharmacodynamic Data**

Serial blood samples for assessment of the percentage of activated CD63+ basophils in peripheral blood will be collected in all subjects in the PK/PD subset at the following times:

- Day 1: 0 hour (morning pre-dose), and 0.25, 0.5, 1, 2, 4, 8 and 12 hours morning post-dose (12-hr sample should be collected prior to the evening dose).

- Day 84 (Week 12): 0 hour (morning pre-dose), and at 0.25, 0.5, 1, 2, 4, 8, and 12 hours.

Absolute and percentage change from baseline (CFB) in activated CD63+ basophils will be listed by treatment, day and sampling time. Individual change from baseline in CD63+ data will be plotted for each treatment versus time on linear scales using actual times.

Absolute and percentage change from baseline in CD63+ basophils will be summarized by time point for each treatment and day using the following descriptive statistics: n, mean, SD, CV, median, minimum and maximum. Mean percentage change from baseline in CD63+ basophils will be plotted versus time by treatment and day using nominal times on linear scales.

### **11.3. Pharmacodynamic Parameters**

The following PD parameters will be estimated on Day 1 and 84 using change from baseline in activated CD63+ basophils in peripheral blood using actual sampling times via non-compartment analysis using Phoenix WinNonlin® version 6.4 or higher:

$E_{max}$	Maximum effect
$TE_{max}$	Time to achieve maximum effect
$AUEC_{0-tau}$	Area under the effect versus time curve within a dosing interval

Actual PK blood sampling times will be used for the assessment of all PD parameters, and negative baseline-adjusted values will be included in the analysis.

PD parameters will be presented in data listings and summarized separately using the following descriptive statistics for each treatment and analyte (n, mean, SD, CV, minimum, median, and maximum). For  $TE_{max}$ , only n, median, minimum and maximum will be reported.

## **11. Interim Analysis**

An unblinded interim safety and PK data review will be performed by the DMC once the patients in the safety run-in period complete their Day 8 ( $\pm 2$  days) assessments. Patients in the safety run-in period will continue to be dosed whilst the interim analysis is being conducted. However, further enrollment in each treatment group will only resume after safety and PK data of the first week for the first 5 patients are reviewed and considered satisfactory by the DMC.

An independent DMC appointed by the Sponsor will review the interim safety and PK data of the first 5 patients enrolled in the safety run-in period. Further details will be provided in the DMC charter, and a separate Interim Analysis SAP.

## 12. Changes in the Planned Analysis

Change from v0.2 (sponsor mail approved version):

- General: for coding dictionary (MEDDRA, WHODrug), add "or later" wording to apply newest version if needed.
- General: applied changes in Protocol Amendment 3.
- Section 4.2: added baseline definition for platelet count related endpoints
- Section 4.6.3:
  - specified the PD that may impact the analysis will be excluded from PP set.
  - fixed typo for incorrected referring link (Section 7.2.2 -> Section 7.4.2)
- Section 7.4.2: change the source of dose taken
- Section 8: specified the priority of using result when multiple
- Section 8.1.1: specified the scenario when there are missing visit result.
- Section 8.1.2:
  - correct the value round
  - specified the scenario that model fail to converge due to more visits then subjects
- Section 8.2.1: specified the scenario when there is missing visit result.
- Section 8.2.2: specified the scenario that model fail to converge due to more visits then subjects or imputed value out of range.
- Section 8.2.3: specified the visit/date used for time to response.
- Section 9.3:
  - corrected used results. Both central and local lab results will be used.
  - removed the clinically significant since it's not applicable for this study.
  - removed the platelet count in choosing records when multiple.
  - removed the redundant description
- Section 9.4: removed the clinically significant since it's not applicable for this study.

Change from v1.0 (sponsor approved version)

- Section 7.4.2: Aligned compliance calculation using Subject Diary as resource

## 14. Appendices

### 15.1. Schedule of Events

The total study duration will be 20 weeks per patients, which consists of up to 4 weeks of screening period. The treatment period will be 12 weeks (split into 1-week safety run-in period and 11-week treatment period for the first 5 patients). The post-treatment follow-up period will be of 4 weeks. Each assessment will be carried out at timepoints indicated in the Schedule of Events table and clarified in the footnotes presented below the table. The schedule of events is summarized in Table 15-1.

Table 15-1 Schedule of Events

		On-treatment Visits					Follow-up Clinic Visits	Early Withdrawal/ Unscheduled visit
	Screening (D-28 to D-1)	W1 (D1), W5 and 9 ( $\pm 3$ days)	W1D4 ( $\pm 1$ days)	W2D8 ( $\pm 2$ days)	W3, 7, 11 ( $\pm 3$ days)	W12 (D84) (EOT) ( $\pm 3$ days)	End of Study W16 ( $\pm 1$ week)	
Clinic visits	X	X a		X a*	X a	X a	X a	X
Informed consent	X							
Inclusion/Exclusion criteria	X	X h						
AEs	<----->							X
Concomitant medications	X	X		X*	X	X	X	X
Height	X							
Weight	X	X		X*		X	X	X
Physical examination/medical history b	X	X		X*	X	X	X	X
ECG c	X	X		X		X	X	X
Vital signs	X	X		X*	X	X	X	X
Urinalysis	X	X		X*	X	X	X	X
Hep B & C, HIV	X							
Pregnancy test/ FSH d	X							
Contraception status	X	X		X*		X	X	X
ABO and Rh blood type	X							
Serum chemistry	X	X		X*	X	X	X	X
Hematology, differential	X	X	X a,e	X a,e	X	X	X	X
PT/INR PTT	X					X		

		On-treatment Visits					Follow-up Clinic Visits	Early Withdrawal/ Unscheduled visit
	Screening (D-28 to D-1)	W1 (D1), W5 and 9 ( $\pm 3$ days)	W1D4 ( $\pm 1$ days)	W2D8 ( $\pm 2$ days)	W3, 7, 11 ( $\pm 3$ days)	W12 (D84) (EOT) ( $\pm 3$ days)	End of Study W16 ( $\pm 1$ week)	
Study drug dispensing		X			X			X f
Study drug administration		X	X	X*	X	X		X f
Blood samples for PK and PD assessments g		X h		X*		X		
Bleeding Score i		X		X*		X	X	X
Quality of life using SF-36 score		X				X	X	X
Pharmacogenomic screening j		X						

Abbreviations: AEs, adverse events; D, Day; ECG, 12-lead electrocardiogram; EOT, end-of-treatment; FSH, follicle stimulating hormone; hep, hepatitis; HIV, human immunodeficiency virus; PD, pharmacodynamics; PK, pharmacokinetics; PT/INR, prothrombin time/international normalized ratio, PTT, partial thromboplastin time; W, Week

- \* Patients in the safety run-in period will have clinic visit on Week 2/Day 8 ( $\pm 2$  days) for the mentioned assessments including hematology (differential) tests. For other patients, this visit will be laboratory only visit to perform hematology (differential) tests only.
- a Clinic / laboratory visit windows are about  $\pm 3$  days for all dosing period and laboratory visits and about  $\pm 1$  week for clinic follow-up visits. The W12/D84 (EOT) visit should be performed while on therapy.
- b Complete physical examination at Screening and abbreviated physical examination at other visits.
- c For all patients: ECG on the first day of dosing and on Day 1 of each subsequent week as specified in the table above. For patients in the safety run-in only: ECG on the first day of dosing at 1, 2, 4, 8, and 12 hours after the study drug administration.
- d For women of childbearing potential only: Serum pregnancy tests are performed at Screening. FSH testing is needed for post-menopausal female patients only.
- e Laboratory only visits will be performed on Day 4 (Week 1) for all patients and on Week 2/Day 8 ( $\pm 2$  days) for patients other than those enrolled in the safety run-in period.
- f Study drug dispensing and administration can occur at unscheduled visit.
- g Samples to be collected as follows:
  - For the patients in the safety run-in period only (for PK only; no PD assessments):
    - Day 1: morning predose, 0.25, 0.5, 1, 2, 4, 8, and 12 hours (evening predose).
    - Day 8 ( $\pm 2$  days): morning predose, 0.25, 0.5, 1, 2, 4, 8, and 12 hours (evening predose).
    - Week 12: morning predose, 0.25, 0.5, 1, 2, 4, 8, and 12 hours.
  - For the patients in the PK/PD subset only (for PK/PD):
    - Day 1: morning predose, 0.25, 0.5, 1, 2, 4, 8, and 12 hours (evening predose).
    - Week 12: morning predose, 0.25, 0.5, 1, 2, 4, 8, and 12 hours.
  - For other patients not included in the safety run-in period or PK/PD subset (for PK only):
    - Week 12: morning predose.
- h Only on Day 1 (Week 1).
- i Bleeding score assessment as described by [Page](#) et al 2007 should be performed on Day 1 of each week specified in the above table and at follow-up visit.
- j A blood sample for genotyping will be drawn at baseline (Day 1, before dosing) from patients who have consented to participate in the genetic analysis component of the study.
